7.2. Analysis Sets

7.2.1. Safety Population

The Safety Population will consist of all subjects who receive at least one full or partial dose of study treatment (all treated subjects) in Treatment Period 2. This population will be used for all safety reporting. Safety data will be reported separately for subjects in Treatment Period 1 who do not go on to Treatment Period 2, and for those subjects in Treatment Period 1 who are treated in both periods.

7.2.2. Full Analysis Set (FAS)

The FAS will consist of all subjects treated in Period 2 who either undergo a CT or MRI scan with tumor assessment at Visit 4 (i.e. they have not discontinued treatment prior to Visit 4) or those who have discontinued Treatment Period 2 prior to Visit 4 solely due to documented disease progression. This population will be used for efficacy evaluation.

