	
quintiles, number of valid cases for continuous variables and n, frequency and percentage for categorical variables with 95% confidence limits, when appropriate).
 
All subjects who received a full or partial dose of the study drug (in Treatment Period 2) on at least one occasion are considered evaluable subjects for safety analysis. All treated subjects in Treatment Period 2 who also undergo a CT or MRI scan with tumor assessment after 12 weeks, or who discontinue treatment prior to 12 weeks solely due to disease progression, will be included in the Full Analysis Set (FAS), which will be used for the efficacy evaluation. The Per Protocol population (all FAS subjects, excluding those for whom major protocol violations have been identified) will be used in the sensitivity analyses for all secondary efficacy endpoints.
 
The ODCR will be determined as the proportion of treated subjects who have achieved SD, PR or CR. The ORR will be determined as the proportion of treated subjects who have achieved CR or PR. Estimates of the ORR and the ODCR will be presented with the corresponding 95% confidence interval. PFS, duration of stable disease, and OS will be analyzed using the Kaplan-Meier method. The Kaplan-Meier survival curves will be plotted. OS is defined as the time from the first dose of study drug (beginning of Treatment Period 2) until the date of death from any cause. Subjects who do not die will be censored for this analysis at the last documented date at which the subject is known to be alive. PFS is defined as the time from the first dose of study drug (beginning of Treatment Period 2) until objective tumor progression or death. Medians for time to event variables will be presented with the corresponding 95% confidence intervals.

Interim Analysis	
Interim analysis will be performed for the primary efficacy endpoint (ODCR) once the first tumor assessment during Treatment Period 2 is completed for at least 20 enrolled subjects. An interim analysis of all efficacy endpoints (with the exclusion of overall survival) may also be performed once all enrolled subjects have entered the Follow-up Period and are being followed for overall survival. Analysis of all safety endpoints will also be included in any interim analyses.

Number of Study Centers (and Locations) Planned	
Up to 50 study sites in the US and Europe are planned for enrollment.

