Symptomatic Deterioration: Subjects with a global deterioration of health status requiring discontinuation of treatment in Treatment Period 2 without objective evidence of disease progression at that time should be classified as having symptomatic deterioration. Reasonable efforts should be taken to obtain radiographic evidence to confirm disease progression. Subjects experiencing symptomatic deterioration during Treatment Period 1 are ineligible to enter Treatment Period 2 (as they do not meet the inclusion criteria requiring radiographic evidence of progression).

The baseline sum of diameters (from the Screening Visit) will be used as reference to further characterize disease control in the measurable dimension of the disease to determine the eligibility to continue participation in Treatment Period 2 of the study. From that point onward, the scan that led to those subjects' termination of Treatment Period 1 and eligibility to enter Treatment Period 2 will serve as a subject's new "baseline" measurements, with that sum of diameters used as reference to characterize the objective tumor response. CR and PR are defined as Objective Responses and must be confirmed by repeat assessment performed at least four weeks after the criteria for response are first met.

Table 12. Evaluation of Time Point Response: Patients with target (+/- non-target) disease*

Target Lesions	Non Target Lesions	New Lesions	Overall Response	Confirmation Scan (Treatment Period 2 only)
CR	CR	No	CR	Yes
CR	Non CR/Non PD	No	PR	Yes
CR	Not Evaluated	No	PR	Yes
PR	Non CR/Non PD/Not Evaluated	No	PR	Yes
SD	Non CR/Non PD	No	SD	No
PD	Any	Yes or No	PD	No
Any	PD	Yes or No	PD	No
Any	Any	Yes	PD	No

*Derived from *New Response Evaluation Criteria in Solid Tumours: Revised RECIST guideline (version 1.1)*, **Table 1, 2 & 3**

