7. STATISTICAL METHODOLOGY

7.1. Sample Size

The primary objective of the study is to evaluate the efficacy of the study drug by the frequency of subjects with overall disease control (including SD, PR, and CR).

The null hypothesis assumes an historical disease control rate of <5%, given that these subjects have already failed progestin therapy. A clinically significant difference is predefined as a 15% increase (i.e. disease control rate of 20%). Using the Fleming's single stage procedure (in which a predetermined number of patients is recruited to the study and a decision about activity is obtained from the number of responses (including SD, PR, or CR) amongst these patients) with the probabilities of type I and type II errors of 5% (one-sided) and 10%, respectively, approximately 40 subjects are planned to be enrolled to Treatment Period 2. It is estimated that approximately 20-25% of subjects will be classified as PrR negative and go directly into Treatment Period 2. This group will represent 14-16 of the Treatment Period 2 subjects. The rate of subjects who will have progressive disease following treatment with megestrol acetate in Treatment Period 1 and then move on to Treatment Period 2 is estimated at 55-60%. These subjects will represent 30-32 of the Treatment Period 2 subjects (estimating that approximately 24-25 subjects treated in Treatment Period 1 will not exhibit progressive disease and will not move into Treatment Period 2.) Estimating the rate of subjects who will be unavailable for disease assessment for various reasons at 10-15%, it is planned to enroll 72 total subjects. An estimated 20% screen failure rate will require up to 90 screened patients to allow for enrollment of 72 subjects.

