7.4. Analysis of Efficacy

The Full Analysis Set will be used for all efficacy analysis. The Per Protocol Set will be used for supportive analysis of all efficacy parameters.

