8.2 Full Analysis Set

The Full Analysis Set (FAS) will consist of all Safety Population subjects treated in Treatment Period 2 who either undergo a tumor assessment at Visit 4, Week 12 (i.e. they have not discontinued Treatment Period 2 prior to Visit 4, Week 12) or those who have discontinued Treatment Period 2 prior to Visit 4, Week 12 solely due to documented disease progression since Treatment Period 2 dosing started. This population will be used for efficacy evaluation.

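### The efficacy listings are restricted to a Full Analysis Set that drops treated Period 2 subjects without a Week 12 assessment or documented progression, although the SAP text promises best response, PFS and OS for every Period 2 subject

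*Protocol*

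**What the plan says.** **Who is in the FAS.** Protocol 7.2.2 takes treated Period 2 subjects with a scan at Visit 4, plus "those who have discontinued Treatment Period 2 prior to Visit 4 solely due to documented disease progression". The synopsis has the same rule ("or who discontinue treatment prior to 12 weeks solely due to disease progression, will be included in the Full Analysis Set (FAS"). SAP 8.2 keeps it, with early stoppers admitted only if they stopped "solely due to documented disease progression since Treatment Period 2 dosing started". The Per Protocol Set is a subset of the FAS, so it recovers nobody.

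**What the FAS is used for.** Protocol 7.4: "The Full Analysis Set will be used for all efficacy analysis". The synopsis words the rates differently: "The ODCR will be determined as the proportion of treated subjects who have achieved SD, PR or CR", and "The ORR will be determined as the proportion of treated subjects who have achieved CR or PR".

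**Who was expected to fall out.** Protocol 7.1 plans for losses: "Estimating the rate of subjects who will be unavailable for disease assessment for various reasons at 10-15" percent. Protocol 5.6.2 foresees women who stop treatment because of declining health without objective progression; they "should be classified as having symptomatic deterioration".

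**What the SAP will produce.** SAP 1 says that the SAP's methods replace the protocol's. The study is closing early: no test is planned (SAP 3.5), ODCR and ORR are not calculated (SAP 14.4, 14.5), and the output is listings, one ECG table and a swimmer's plot. SAP 14 says that best overall response, PFS and OS will be listed for each Period 2 subject, with duration of stable disease where it applies. SAP 14.3 determines best response for every Period 2 participant and draws the swimmer's plot on all Safety Population subjects in Period 2. SAP 25 puts listings 16.2.6.1 to 16.2.6.7 on the FAS.

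**The concern.** Entry to the efficacy set depends on what happens after treatment starts. A woman is kept if she reaches the Week 12 scan or has progression documented before it, and dropped if she stops for another reason. On the literal wording, a woman still on treatment who misses the Visit 4 scan is dropped too.

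In a report built almost wholly on listings, the listing population is the analysis. If anyone is excluded, the SAP text and the figure cover her but the efficacy listings do not. Her lesion data, tabulated best response, PFS and OS, and censoring status would appear nowhere. Yet the protocol asks for scans to continue after a stop for reasons other than progression (5.6) and for survival status on everyone leaving Period 2 (5.1.4).

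A second, conditional matter is that any rate or survival estimate on the FAS would flatter the treatment if the excluded women do worse than the assessed ones.

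**Working it through.** **1. SAP text against listing headers.**

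| Item | Subjects covered |
|---|---|
| SAP 14, best response, PFS, OS | each Period 2 subject |
| SAP 14.3, best response | each Period 2 participant |
| SAP 14.3 and 24, swimmer's plot | Safety Population subjects in Period 2 |
| SAP 9.6, efficacy reporting groups | include all Period 2 subjects |
| SAP 14.7, PFS | death from any cause is an event; undeterminable best response is censored |
| SAP 25, listings 16.2.6.1 to 16.2.6.7 | FAS only |

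Take a woman who dies in Week 8 of Period 2 with no scan showing progression. Under SAP 14.7 she has a PFS event and under SAP 14.8 an OS event. Under SAP 8.2 she is outside the FAS, so neither listing shows her. SAP 14.7 also censors women whose best response cannot be determined, most of whom the FAS has already removed. SAP 14.5 counts women unassessed for safety reasons as non-responders, although those who stopped early are likewise gone. SAP 20, which records the changes from the protocol, does not mention any of this.

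**2. How many women.** Inputs: 25 enrolled (SAP 4.5); share PrR negative a = 0.20-0.25, share of the rest progressing into Period 2 b = 0.55-0.60, share unavailable for assessment d = 0.10-0.15 (protocol 7.1, SAP 6). Assumption: these planning rates held, and d stands in for the share that the FAS drops.

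- Period 2 entrants = 25a + 25(1 − a)b. Low: 5 + 11 = 16. High: 6.25 + 11.25 = 17.5.
- Excluded = entrants × d. Low: 16 × 0.10 = 1.6. High: 17.5 × 0.15 = 2.6. About 2 to 3 women.
- Chance that nobody is excluded: 0.90^16 = 18.5% down to 0.85^17.5 = 5.8%.

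**3. The plan's own sample size.** Null rate 5%, target 20%, one-sided type I error 5%, power 90%. The smallest exact single-stage design is n = 38 with at least 5 controlled (type I error 4.0%, power 90.1%). At n = 40 with the same cut-off these are 4.8% and 92.4%. The stated figure of about 40 is reproduced.

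**4. What the FAS does to a rate (protocol as written).** Let q be the FAS rate and c the control rate of excluded women as a multiple of q. The all-treated rate is q[(1 − d) + dc]. With q = 20.0%:

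| c | d = 0.10 | d = 0.15 |
|---|---|---|
| 0 (none controlled) | 18.0% | 17.0% |
| 0.5 | 19.0% | 18.5% |
| 1 | 20.0% | 20.0% |
| 1.5 | 21.0% | 21.5% |

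The lean is upward only when c is below 1. SAP 10.1 gives eight reasons other than progression for stopping Sodium Cridanimod. Three (adverse event, death, concurrent illness) are plainly unfavourable, and no frequencies are given. A c below 1 is therefore likely but not certain; a woman with stable disease on an early scan who then withdraws would push the other way. The documents give nothing from which to size a bias in PFS or OS.

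**The case against.** **The rates are cancelled.** The SAP computes no ODCR or ORR and says that the sample size calculations no longer apply. This stands. A reader might infer that the FAS rule inflates the error of the trial's primary test, but no test will be run, and even protocol 7.4.1 plans only an estimate with a confidence interval.

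**A new decision cut-off.** A reader might conclude that an all-treated analysis of 44-48 women (14-16 plus 30-32, protocol 7.1) should use a cut-off of 6. The documents do not support that. They state no cut-off, only 25 women were enrolled, and the result depends on what the 20% target refers to. If it is an all-treated rate, power at a cut-off of 6 is 89.8% (n = 44) to 93.8% (n = 48). If it is a rate among assessed women, the all-treated target is 17-18% and power is 78-83% (n = 44) or 85-89% (n = 48).

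**The synopsis may not contradict protocol 7.4.** Its phrase about treated subjects follows an FAS definition that itself begins with treated subjects, so it may be shorthand for the FAS. This stands: a clash of denominators is one reading, not a settled fact.

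**Much can be recovered.** The swimmer's plot shows exposure, response over time, follow-up and best response for every Period 2 subject. Listing 16.2.7.7 gives mortality, and 16.2.3 gives the analysis populations, with reasons for exclusion (SAP 10.2). This reduces the loss but does not remove it: lesion measurements and tabulated PFS and OS with censoring are still missing.

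**SAP 9.6 may only name display groups.** That is fair, but SAP 14 and 14.3 carry the conflict without it.

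**Conclusion.** The point holds for the listings and should be fixed. The FAS-only headers cannot be reconciled with SAP 14, 14.3 and 14.7 if any treated Period 2 subject is outside the FAS. Following the headers would omit early deaths without documented progression from the PFS and OS listings. The size is small in numbers: about 2 to 3 women if the planning rates held in a study that closed early, and possibly none. The documents do not give the actual count.

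The upward lean in ODCR, ORR, PFS and OS is conditional on excluded women doing worse, and it matters only if such an estimate is ever reported. At its most unfavourable under the planning rates (none controlled), a FAS rate of 20.0% is 17-18% of all treated.

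**What to change.** 1. In SAP 25, put listings 16.2.6.4 to 16.2.6.7, and the Period 2 data in 16.2.6.1 to 16.2.6.3, on all subjects treated in Period 2 (the swimmer's plot population), with a column flagging FAS membership. Record the change in SAP 20.
2. Since SAP 14.7 censors PFS at the last Period 2 assessment, add one line saying which date applies to a woman who has none.
3. If any ODCR or ORR is calculated, use all treated Period 2 subjects as the denominator. Count women without a qualifying stable disease or response as not controlled, and those without a confirmed response as non-responders. This agrees with SAP 14.5 and with section 4.9.1 of the appended RECIST 1.1 guideline, which, for trials with response as primary endpoint, advises against resting conclusions on an evaluable subset. Keep the present FAS as a supportive evaluable set.
4. Separately, delete the leftover sentence in SAP 14.8 promising Kaplan-Meier curves and medians on the FAS and PPS. It contradicts the statements in SAP 14.6 to 14.8 that no medians will be calculated, and SAP 8.3, which says that the PPS no longer applies.

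The cost is SAP wording and listing headers, with no new data. No protocol amendment is needed, because the SAP already supersedes the protocol's methods. The downside is that any rate calculated would probably be slightly less favourable. If nobody was excluded, the listed subjects do not change.

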7.2.3. Per Protocol Set (PPS)

The Per Protocol Set will consist of all FAS subjects, excluding those for whom major protocol deviations have been identified. This population will be used for supportive analysis of the response rate and other efficacy parameters.

7.3. Demographics and Other Baseline Characteristics

A descriptive analysis approach will be used to analyze all demographic and baseline characteristics and will be presented using appropriate summary statistics (mean, standard deviation, median, minimum, maximum, range, quintiles, frequency and percentage for categorical variables with 95% confidence limits etc., when appropriate). The Safety Population will be used to present all demographic and baseline characteristics.

7.4. Analysis of Efficacy

The Full Analysis Set will be used for all efficacy analysis. The Per Protocol Set will be used for supportive analysis of all efficacy parameters.

7.4.1. Analysis of Primary Objective

The primary objective of this study is to evaluate the efficacy of the study drug by the frequency of subjects with overall disease control (including SD, PR, and CR).

The ODCR will be determined as the proportion of subjects who achieved SD, PR and CR during Treatment Period 2. The ODCR will be estimated and presented with the corresponding 95% confidence interval.

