3.5 Statistical Hypotheses

As this is a Phase 2, single-arm open-label study, no formal hypothesis testing is planned. The abbreviated analyses will consist of listings and one electrocardiogram (ECG) table with descriptive statistics.

4. Study Design and Procedures

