14.4 Overall Disease Control Rate

The ODCR will be determined as the proportion of subjects who achieved CR, PR or SD as their best overall response during Treatment Period 2 in accordance with RECIST 1.1 criteria, relative to the efficacy population. The ODCR will be summarized by number and percentage of subjects meeting the definition of ODCR along with the corresponding exact 2-sided 95% confidence interval (CI). ODCR will not be calculated or presented for Treatment Period 1.

Since the study is closing early, no calculation of ODCR will be made.

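### Does reporting the disease control rate with a 95% confidence interval undercut a design sized for a one-sided 5% test with 90% power?

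*Protocol*

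**What the plan says.** Protocol 7.1 names Fleming's single-stage procedure for Treatment Period 2. It sets a null disease control rate of 5%, a target of 20%, and "with the probabilities of type I and type II errors of 5% (one-sided) and 10%, respectively, approximately 40 subjects are planned to be enrolled". It also gives the basis for the conclusion: "a decision about activity is obtained from the number of responses". SAP section 6 repeats the design, names A'Hern's exact version of it, and makes the 40 those who contribute to the primary analysis. Neither document states the critical count.

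For the analysis, Protocol 7.4.1 says "The ODCR will be estimated and presented with the corresponding 95% confidence interval". SAP 14.4 makes that interval exact and two-sided. SAP 3.5 says that "no formal hypothesis testing is planned". SAP 9.2 also says that nothing will be tested, yet describes Fleming's procedure as a one-sample test of a proportion with a single primary hypothesis.

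The SAP was written after the decision to close the study. It supersedes the protocol's methods (section 1), says that none of the protocol objectives will be analysed (section 2), records 25 women enrolled (4.5), calls the sample size calculations no longer applicable (section 6) and cancels the calculation of the disease control rate (14.4).

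**The concern.** Read alone, Protocol 7.4.1 seems to replace the test behind the sample size with a stricter one. A two-sided 95% interval whose lower limit must clear 5% is a one-sided test at 2.5%, half the 5% used for sizing. With no critical count written down, and a statement in SAP 3.5 that nothing is tested, a reader could conclude that the interval is the only criterion.

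The two readings conflict at the design's own boundary. With 5 of 40 patients controlled, the one-sided test rejects 5%, while the exact 95% interval still contains it. The treatment could then be called active or inactive depending on which section is followed, and the planned 10% type II error would be about 16% under the interval reading.

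**Working it through.** **Inputs.** Null rate p0 = 0.05, target p1 = 0.20, one-sided type I error 0.05, type II error 0.10, n about 40 (Protocol 7.1, SAP section 6). Interval: exact, two-sided, 95% (SAP 14.4).

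**Step 1: the plan's sample size.** For a cut-off r, type I error is P(X ≥ r | n, p0) and power is P(X ≥ r | n, p1), with X binomial. The smallest n that meets both targets is 38 with r = 5 (type I error 0.0397, power 0.9014). At n = 40:

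| Cut-off | Type I error | Power |
|---|---|---|
| ≥4 | 0.1381 | 0.9715 |
| ≥5 | 0.0480 | 0.9241 |
| ≥6 | 0.0139 | 0.8387 |

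The smallest count that keeps type I error at or below 5% is 5, and it gives more than 90% power. The figure of about 40 reproduces, and the unwritten cut-off follows uniquely from the stated inputs.

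**Step 2: the interval read as a test.** The exact (Clopper-Pearson) lower limit for x of n is the α/2 quantile of Beta(x, n − x + 1).

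- 5 of 40, 95% interval: 4.19% to 26.8%, which contains 5%.
- 6 of 40, 95% lower limit: 5.71%, which excludes 5%.
- 5 of 40, 90% lower limit: 5.06%, in agreement with the one-sided 5% test.

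So the interval reading needs 6 of 40, with type II error 1 − 0.8387 = 16.1%, against 1 − 0.9241 = 7.6% for the count rule. The two disagree on one outcome, exactly 5, which has probability 0.9241 − 0.8387 = 8.5% at a true rate of 20%.

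**Step 3: the likely number evaluable.** Protocol 7.1 expects 14-16 plus 30-32 patients in Treatment Period 2, that is 44 to 48, and 10-15% without a disease assessment. If that loss applies to those entering Treatment Period 2, 44 × 0.85 = 37.4 and 48 × 0.90 = 43.2, so about 37 to 43.

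| n | Count rule: cut-off, power | 95% interval as test: cut-off, power |
|---|---|---|
| 37 | 5, 0.888 | 6, 0.778 |
| 38 | 5, 0.901 | 6, 0.800 |
| 39 | 5, 0.913 | 6, 0.820 |
| 40 | 5, 0.924 | 6, 0.839 |
| 41 | 6, 0.856 | 6, 0.856 |
| 42 | 6, 0.871 | 6, 0.871 |
| 43 | 6, 0.885 | 6, 0.885 |

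The rules differ only at 37 to 40. Power below 90% at 41 to 43 comes from the discreteness of the binomial and is the same under both.

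**Step 4: the interval method.** Protocol 7.4.1 names none. Used as a test at n = 40, a Wilson interval excludes 5% from 5 patients (lower limit 5.46%, power 92.4%) and a Wald interval only from 7 (5.72%, power 71.4%). The 84% is therefore tied to the exact method of the SAP as well as to the added rule that the lower limit must exceed 5%.

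**The case for a change.** The strongest argument for a change is that a single-stage design is its cut-off, and a plan that says the decision rests on a count should state the count. The RECIST guideline appended to the protocol (section 2) asks protocols to define the decision criteria as well as the sample size. The cut-off moves from 5 to 6 inside the expected range of evaluable patients, so fixing it in advance for each n has practical use. SAP 3.5 justifies the absence of testing by the phase and the single-arm design, not by early closure, which sits badly with section 6. Writing the rule down would take a few sentences.

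This stands as a remark on completeness, but it does not show lost power or a second decision rule. The interval is described as something to estimate and present, and Protocol 7.4.2 uses the same form of words for the objective response rate, which has no hypothesis attached. A two-sided 95% interval beside a one-sided design is ordinary reporting, and section 4.9.1 of the appended guideline prefers such limits for response rates. The sentence after the one quoted from SAP 3.5 describes the abbreviated output of listings and one ECG table, so it is weak evidence of how the full trial would have been judged.

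**Conclusion.** No change is needed. The design named in the protocol delivers its stated error rates at 40 evaluable patients: at least 5 controlled, type I error 4.8%, power 92.4%. The figure of about 84% appears only if a reader adds a success criterion that neither document contains, and even then the readings part only at 37 to 40 evaluable patients, over a result of exactly 5. The gap is a derivable number left unwritten, which an analyst would fill from the stated design by the exact one-sided rule: 5 for 37 to 40 patients, 6 for 41 to 48.

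This rests on taking 5% as the null boundary and on reading the interval as descriptive, which is what its wording supports. Early closure settles the practical side. With 25 women enrolled in all, 40 evaluable patients in Treatment Period 2 cannot occur, and the SAP will not compute the disease control rate, so a written cut-off would alter no reported result or conclusion.
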